1.7 Operational Definition of Key Terms

Cerebral Palsy (CP):

A group of permanent disorders affecting the development of movement and posture, causing activity limitations, that are attributed to non-progressive disturbances occurring in the developing fetal or infant brain. While the injury itself is non-progressive, the resulting neuromuscular and musculoskeletal impairments, such as tone abnormalities,

joint contractures, and motor coordination deficits, may evolve over time. (Blair & Cans, 2025; Panda et al., 2024)

Spastic CP:

The most common type of cerebral palsy, characterized by increased muscle tone (hypertonia), stiffness, and restricted joint movement.(Novak et al., 2012)

Equine's Deformity:

A musculoskeletal condition commonly observed in children with spastic CP, involving excessive plantarflexion of the ankle, which impairs gait and balance.(İğrek et al., 2022)

Achilles Tendon Lengthening Surgery:

A surgical procedure performed to release or elongate the Achilles tendon to correct equinus deformity and improve ankle dorsiflexion.

Conventional Physiotherapy:

A structured rehabilitation program including stretching, strengthening, gait training, and balance exercises delivered by a licensed physiotherapist.

Myofascial Release (MFR):

A hands-on manual therapy technique aimed at relieving fascial restrictions to improve range of motion, reduce pain, and enhance movement efficiency.(Ajimsha et al., 2015b)

Chapter Two: Conceptual Framework and Literature Review

2.1 Conceptual Framework

Cerebral palsy (CP) is a group of permanent movement disorders caused by non-progressive disturbances in the developing fetal or infant brain. These neurological impairments frequently result in spasticity, joint contractures, and musculoskeletal deformities—most notably equinus foot due to gastrocnemius-soleus spasticity. Surgical interventions such as Achilles tendon lengthening are often employed to correct these deformities and improve gait. However, postoperative outcomes depend heavily on the quality of rehabilitation.

Conventional physiotherapy (CPT) is the cornerstone of post-surgical rehabilitation. It aims to improve muscle strength, range of motion (ROM), balance, and gross motor function through structured exercises and task-specific training. However, conventional techniques may not adequately address soft tissue and fascial restrictions that persist after surgery.

Myofascial Release (MFR) is a manual therapy technique that applies gentle, sustained pressure to fascial structures to reduce adhesions and restore tissue extensibility. When integrated with CPT, MFR may enhance the effectiveness of rehabilitation by improving tissue flexibility and reducing muscle tone, thereby allowing better engagement with physiotherapy exercises.

2.1.1 Independent Variables

Conventional Physiotherapy

This includes standard rehabilitation interventions provided to children with cerebral palsy post-Achilles tendon surgery. It typically consists of stretching, strengthening, balance training, and gait re-education to improve functional outcomes.

MFR

A manual therapy technique applied to the fascia and soft tissues to reduce tightness, improve tissue mobility, and support better functional movement. When added to conventional physiotherapy, it is hypothesized to enhance motor recovery and joint mobility.

2.1.2 Dependent Variables

Gross Motor Function

This refers to a child's ability to perform large muscle activities, such as sitting, standing, and walking. It will be measured using the Gross Motor Function Measure (GMFM), a validated scale for children with CP.

[figure not shown]
Range of Motion (ROM)

Specifically focused on ankle dorsiflexion and plantarflexion, ROM will be measured using a goniometer to assess joint mobility post-surgery and throughout rehabilitation. Improved ROM is essential for better gait and balance.

Balance:

The ability to maintain upright posture and stability during static and dynamic tasks. It will be measured using the Pediatric Balance Scale (PBS), a validated tool for young children with CP.

In this study, the independent variables—CPT and MFR—are expected to influence the dependent outcomes: gross motor function, balance, and ankle ROM. MFR is hypothesized to enhance the structural readiness of muscles and fascia, reducing tone and improving tissue mobility. This, in turn, may augment the efficacy of CPT by enabling more effective execution of strengthening, balance, and gait exercises. The synergistic combination is thus anticipated to yield greater improvements in functional outcomes compared to CPT alone.

Conceptual framework (Self developed)

2.2 Literature Review

CP is one of the most prevalent motor disorders affecting children worldwide, characterised by spasticity, muscle stiffness, impaired motor control, and poor functional mobility. Numerous interventions have been proposed to enhance motor function and quality of life in children with CP, among which MFR has gained increasing attention as a complementary technique to conventional physiotherapy. This literature review explores existing evidence on the effectiveness of MFR and related interventions, particularly after Achilles tendon lengthening (ATL) surgery, and highlights current gaps in the research.

(Khanna et al., 2023) Compared Neurodevelopmental Therapy (NDT) alone to NDT combined with MFR in children with spastic CP. The study found that the combined therapy group demonstrated significantly greater improvements in gross motor function, as measured by GMFM-88, suggesting that MFR may enhance the outcomes of conventional approaches.

(Avilash Mohapatra et al., 2024) Investigated the comparative impact of MFR and Deep Oscillation Therapy (DOT) on hamstring flexibility and muscle tone. Their results showed that both techniques effectively reduced spasticity and improved ROM, with MFR being slightly more effective.

(Paul et al., 2018) focused on MFR's effectiveness in reducing hamstring spasticity among diplegic CP children. The findings confirmed that MFR significantly decreased spasticity and enhanced knee ROM, thus supporting its inclusion in pediatric CP rehabilitation programs.

(Curtis et al., 2018) evaluated the effects of trunk and head control training on functional changes in children with CP. The study highlighted improvements in gross motor function, emphasizing the importance of integrated therapeutic strategies.

(Kwan et al., 2023) explored the biomechanical impact of tendon release surgery on gait and stiffness control in spastic diplegic CP children. Post-surgical improvements in inter-limb leg stiffness were observed, indicating that ATL surgery positively influences gait mechanics but still requires adjunctive therapy for optimal results.

(Horsch et al., 2022) provided a meta-analysis on the recurrence of equinus deformity following ATL in CP patients. The recurrence rate was significant, underlining the necessity for effective postoperative rehabilitation methods such as MFR.

(Usta Ozdemir et al., 2024) Presented a case report involving electromyographic biofeedback training post upper limb tendon transfer surgery in a CP patient. The intervention yielded functional improvements, illustrating the benefit of integrating novel physiotherapy techniques.

Dietz et al. (2006) provided a medium-term follow-up of patients after ATL surgery. Despite improvements in ankle ROM, continued physiotherapy was deemed essential to sustain functional gains, reinforcing the role of adjunctive therapies.

[figure not shown]
In summary, while existing literature demonstrates the potential benefits of MFR in improving gross motor function and ROM in children with CP, few studies have directly examined its effect post-Achilles tendon surgery. Most research has been limited by small sample sizes, short follow-up periods, or lack of standardized protocols. This gap underscores the need for further investigation into the combined use of MFR and conventional physiotherapy, particularly in the post-surgical context. The present study aims to address this gap by evaluating the effectiveness of adding MFR to conventional therapy on gross motor function and ROM in pediatric CP patients post-ATL in the Gaza Strip.

Chapter Three: Materials and Methods

3.1 Study design

A single-blind randomized controlled trial (RCT) will be conducted to evaluate the effect of adding Myofascial Release (MFR) to conventional physiotherapy on functional outcomes in children with cerebral palsy after Achilles tendon surgery. Participants will be randomly assigned to either an intervention group (MFR + physiotherapy) or a control group (physiotherapy only). Assessments will be conducted at baseline and after 8 weeks of intervention.

Flow Diagram

3.2 Setting and Period of the Study

The study will be conducted at The Jerusalem Princess Basma Centre located within Al-

Ahli Al-Arabi Hospital in Gaza, Palestine. This centre is a specialized and well-established

Analysed (n=)

- Excluded from analysis (give reasons) (n=)

Follow up 6

rehabilitation facility that offers multidisciplinary services for children with neuromuscular disorders, including cerebral palsy. It is equipped with qualified rehabilitation professionals, physiotherapy units, and child-friendly environments tailored to the needs of pediatric patients. The center regularly manages post-operative cases of Achilles tendon lengthening, providing an appropriate setting for the implementation of structured physiotherapy programs, including advanced manual techniques such as Myofascial Release (MFR).

The feasibility of conducting the study at this center is considered high due to the presence of skilled staff, consistent patient flow, and administrative support for research activities. The center's rehabilitation protocols and follow-up systems also support the monitoring and documentation required for clinical research. The study period will span from March to August 2025, covering participant recruitment, delivery of the intervention, and pre- and post-intervention data collection.

3.3 Study Population

The study population will comprise children aged 2 years and older who have been diagnosed with spastic CP and have undergone Achilles tendon surgery within the past 3 months. Participants will be sourced from the patient registry at The Jerusalem Princess Basma Centre at Alahli Al-arabi hospital, a specialised rehabilitation centre in Gaza, ensuring they meet the eligibility criteria outlined in section 3.4.

3.4 Eligibility Criteria

Inclusion Criteria:

1. Children aged 2 to 5 years.
2. Diagnosed with spastic cerebral palsy (GMFCS levels I–IV).
3. Have undergone Achilles tendon lengthening surgery within the past 3 months.
4. Medically stable and cleared to begin physiotherapy.
5. Parental/guardian consent to participate in the study.

Exclusion Criteria:

1. Diagnosis of other neuromuscular or developmental disorders.
2. Received Myofascial Release therapy in the past 6 months.

3. Severe cognitive or behavioral impairments that interfere with following instructions.
4. Participation in another rehabilitation study in the past 3 months.

3.5 Sample Size and Sampling Process

A sample size of 40 participants (20 per group) will be targeted, based on feasibility, resource availability, and statistical power considerations. A consecutive sampling method will be employed, selecting eligible participants who consent to participate during the recruitment period.

3.6 Data Collection Procedure

Data collection will be conducted using standardized, validated tools and structured clinical procedures to ensure reliability and accuracy in assessing the functional outcomes of children with cerebral palsy following Achilles tendon lengthening surgery.

3.6.1 Assessment study Tools

The following tools will be used to collect data on the primary outcome measures:

Gross Motor Function Measure-88 (GMFM-88):

This is a standardised observational instrument designed to measure changes in gross motor function in children with cerebral palsy. It consists of 88 items categorised into five dimensions: lying and rolling, sitting, crawling and kneeling, standing, walking, running, and jumping. GMFM-88 has been validated and widely used in pediatric rehabilitation settings (Choi, 2024).

Pediatric Balance Scale (PBS):

An adapted version of the Berg Balance Scale for children, used to assess functional balance in sitting and standing tasks. It consists of 14 items scored on a 5-point scale, and has demonstrated strong validity and inter-rater reliability in children with CP.

Range of Motion (ROM):

Passive ankle dorsiflexion will be measured using a standard universal goniometer. Measurements will be taken with the knee both flexed and extended to assess the length and flexibility of the gastrocnemius-soleus complex. This will provide an objective evaluation of the effect of the interventions on joint flexibility.

3.6.2 Timing of Data Collection

Data will be collected at the following time points:

Pre-Intervention (Baseline):

Before to the start of any physiotherapy sessions, baseline data will be recorded to establish initial levels of function and range of motion.

Post-Intervention (After 8 weeks):

After the completion of the intervention period, a post-treatment assessment will be conducted to measure changes in gross motor function and ankle dorsiflexion ROM.

3.6.3 Data Collectors

Trained physiotherapists who are not involved in the intervention sessions will perform all assessments to avoid bias. They will undergo calibration and training sessions to standardise the assessment procedures and ensure inter-rater reliability.

3.7 Intervention:

This study will include two intervention arms:

3.7.1 Control Group: Conventional Physiotherapy Program

Duration: 8 weeks

Frequency: **3** sessions per week

Session Duration: **45** minutes

Intervention Content:

Passive and active stretching for gastrocnemius-soleus complex

Strengthening exercises for lower limb muscles (especially tibialis anterior and quadriceps)

Balance and postural control training

Functional task training including sit-to-stand, step-ups, and gait training

Use of assistive devices if needed

Objective: To enhance muscle flexibility, improve gross motor performance, and facilitate independence in functional mobility after Achilles tendon lengthening surgery.

3.7.2 Intervention Group: Myofascial Release + Conventional Physiotherapy

Duration: 8 weeks

Frequency: 3 sessions per week

Session Duration: 60 minutes

Intervention Content:

The intervention will be conducted over a period of 8 weeks, with three sessions per week, totaling 24 sessions. Each session will last approximately 60 minutes, divided as follows:

45 minutes for Conventional Physiotherapy (CPT), described above

15 minutes for Myofascial Release (MFR)

Myofascial Release (MFR):

MFR will be administered by a physiotherapist using 4 selected techniques based on individual patient needs and tissue restrictions. Each MFR session will focus on releasing soft tissue restrictions in key muscle and fascial structures involved in gait and postural control in children with spastic cerebral palsy, particularly post Achilles tendon lengthening surgery.

The selected MFR techniques will be drawn from evidence-based protocols described in advanced myofascial release manuals and include:

1. Cross-Hand Release
2. Plantar Fascia Release
3. Gastrocnemius–Soleus Complex Release
4. Hamstring Fascial Lengthening

Each technique will be applied for 2–3 minutes, with gentle, sustained pressure held until tissue "melting" or release is palpated. Sessions will be performed in a calm, supportive environment, ensuring that the child is relaxed and comfortable throughout the treatment.

All sessions will be individualized based on functional level and tolerance, and monitored for consistency and safety.

Rationale: MFR may help release fascial restrictions, improve tissue mobility, reduce muscle tone, and promote better joint ROM and gross motor function—especially after surgical correction.

3.8 Instruments of the Study

To evaluate the functional outcomes of adding Myofascial Release (MFR) to conventional physiotherapy in children with cerebral palsy following Achilles tendon lengthening surgery, the study will utilize the following validated instruments:

3.8.1 Gross Motor Function Measure-88 (GMFM-88)

What it assesses:

Gross Motor Function – the child's ability to perform age-appropriate motor activities such as sitting, standing, crawling, walking, and jumping.

How it will be assessed:

The GMFM-88 includes 88 items divided across five domains:

Lying and Rolling

Sitting

Crawling and Kneeling

Standing

Walking, Running, and Jumping

Each item is scored on a 4-point ordinal scale from 0 (does not initiate) to 3 (completes the task fully). The total and domain-specific scores will be calculated.

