1.5 Research questions

1. Does conventional physiotherapy alone improve gross motor function, balance, and ankle range of motion (ROM) in children with cerebral palsy following Achilles tendon lengthening surgery?
2. Does the addition of Myofascial Release (MFR) to conventional physiotherapy result in greater improvement in gross motor function compared to conventional physiotherapy alone?
3. Does the addition of Myofascial Release (MFR) to conventional physiotherapy result in greater improvement in balance compared to conventional physiotherapy alone?
4. Does the addition of Myofascial Release (MFR) to conventional physiotherapy result in greater improvement in ankle range of motion (ROM) compared to conventional physiotherapy alone?

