3.11 Statistical Management and Procedures

Data will be analyzed using the Statistical Package for Social Sciences (SPSS) version 22. Descriptive statistics will summarize demographic and clinical characteristics. Inferential statistics, such as paired t-tests or Wilcoxon signed-rank tests, will compare pre- and post-intervention scores within groups. Independent t-tests or Mann-Whitney U tests will compare changes between groups. A significance level of $p < 0.05$ will be set for all analyses.

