Appendix

GMFM-88 SUMMARY SCORE

DIMENSION	CALCULATION OF DIMENSION % SCORES			GOAL AREA
(indicated with checkmark)				
A. Lying & Rolling	Total Dimension A 51	= 51	$\times 100 =$	_____ %
B. Sitting	Total Dimension B 60	= 60	$\times 100 =$	_____ %
C. Crawling & Kneeling	Total Dimension C 42	= 42	$\times 100 =$	_____ %
D. Standing	Total Dimension D 39	= 39	$\times 100 =$	_____ %
E. Walking, Running & Jumping	Total Dimension E 72	= 72	$\times 100 =$	_____ %
TOTAL SCORE = $\frac{\%A + \%B + \%C + \%D + \%E}{\text{Total # of Dimensions}}$				
	= 5	=  	=  	%  
GOAL TOTAL SCORE = $\frac{\text{Sum of %scores for each dimension identified as a goal area}}{\text{# of Goal areas}}$				
	=  	=  	%  	

GMFM-66 Gross Motor Ability Estimator Score ¹
GMFM-66 Score =   to   95% Confidence Intervals
previous GMFM-66 Score =   to   95% Confidence Intervals
change in GMFM-66 =  
¹ from the Gross Motor Ability Estimator (GMAE-3) Software

TESTING WITH AIDS/ORTHOSES USING THE GMFM-88

Indicate below with a check (✓) which aid/orthosis was used and what dimension it was first applied. (There may be more than one).

AID	Dimension	Orthosis	Dimension
Rollator/pusher	 _____	Hip Control	 _____
Walker.....	 _____	Knee Control.....	 _____
H Frame crutches	 _____	Ankle-foot Control	 _____
Crutches	 _____	Foot Control	 _____
Quad Cane	 _____	Shoes.....	 _____
Cane	 _____	None	 _____
None	 _____	Other	 _____
Other	 _____	(please specify)	
		(please specify)	

GMFM-88 SUMMARY SCORE USING AIDS/ORTHOSES

DIMENSION	CALCULATION OF DIMENSION % SCORES			GOAL AREA (indicated with ✓ check)
	Total Dimension A	=	× 100 =	
A. Lying & Rolling	51	=	51	% A. 
B. Sitting	60	=	60	% B. 
C. Crawling & Kneeling	42	=	42	% C. 
D. Standing	39	=	39	% D. 
E. Walking, Running & Jumping	72	=	72	% E. 
TOTAL SCORE =	$\frac{\%A + \%B + \%C + \%D + \%E}{\text{Total # of Dimensions}}$			
	=	5	=	%

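### Does leaving the GMFM-88 score for research question 2 unnamed give the trial six chances of a positive answer?

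*Combined protocol and SAP*

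**What the plan says.** Section 1.5, question 2, asks whether adding MFR will "result in greater improvement in gross motor function compared to conventional physiotherapy alone". It names a construct, not a score. Section 2.1.2 is no more specific: "It will be measured using the Gross Motor Function Measure (GMFM), a validated scale for children with CP".

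Section 3.6.1 introduces GMFM-88, PBS and ankle ROM together with the words "The following tools will be used to collect data on the primary outcome measures". Section 3.6.2 says the post-treatment visit is "to measure changes in gross motor function and ankle dorsiflexion ROM".

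Section 3.8.1 describes the instrument ("The GMFM-88 includes 88 items divided across five domains"), gives the item scoring from 0 to 3, and ends: "The total and domain-specific scores will be calculated". It does not rank these scores.

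Section 3.11 compares changes between groups with t-tests or Mann-Whitney tests and adds: "A significance level of $p < 0.05$ will be set for all analyses". It sets out no hierarchy and no adjustment.

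The Appendix reproduces the standard GMFM-88 score form. There the total is the sum of the five dimension percentages divided by 5. The form also has a goal total, a GMFM-66 field, and a second summary under the title "TESTING WITH AIDS/ORTHOSES USING THE GMFM-88".

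**The concern.** A primary outcome measure should lead to one answer. Here one instrument gives six scores, the level is 0.05 for every analysis, and none of the six is tied to question 2. Read strictly, the plan lets an analyst test all six, or settle on one after seeing the results, and call any significant score a yes.

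The choice could matter. Because the total is an average of five dimensions, a clear difference in one domain, such as standing, can sit beside a null total. The plan does not say whether that pattern counts as a positive answer. Section 3.8.2, by contrast, gives the PBS one total out of 56, so the same question does not arise there.

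The form's option of scoring with or without aids and orthoses adds a smaller uncertainty, since the methods do not say which condition is analysed.

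**Working it through.** **Figure in the plan.** There is none to reproduce. The plan states no error rate for question 2, and the target of 40 in section 3.5 comes without an effect size, SD or power.

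**Inputs from the documents.** 20 per arm (3.5); level 0.05 (3.11); 1 total + 5 domains = 6 scores (3.8.1); total = mean of the five dimension percentages (Appendix).

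**Assumptions.** Two-sided tests, normally distributed changes, and a common correlation between dimension changes of 0.3 to 0.9. The documents give no SDs or correlations.

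**Simple bounds if all six are tested.** If independent, 1 − 0.95^6 = 0.265. The upper bound is 6 × 0.05 = 0.30.

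**Allowing for correlation.** Simulation of 100,000 trials per setting, no true effect, t-tests on change with 38 degrees of freedom:

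| Assumed correlation | 0.3 | 0.5 | 0.7 | 0.9 |
|---|---|---|---|---|
| Any of six significant, either direction | 0.217 | 0.186 | 0.151 | 0.103 |
| Any of six favouring MFR | 0.109 | 0.093 | 0.075 | 0.052 |
| Total not significant, at least one domain significant | 0.167 | 0.136 | 0.100 | 0.054 |

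The total alone gives 0.050 in either direction and 0.025 in favour of MFR. A repeat with 40,000 trials per setting gave 0.215, 0.184, 0.151 and 0.100 for the first row. Mann-Whitney tests on the same kind of data gave 0.218, 0.190 and 0.110 at correlations 0.3, 0.5 and 0.9.

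**Where the excess comes from.** At correlation 0.5, 0.050 (total significant) + 0.136 (total null, a domain significant) = 0.186. The whole excess over 5% therefore consists of trials in which a domain is counted as the answer although the total is null. If the total answers the question, the excess is zero.

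**Does the plan commit to counting domains?** Set side by side, the texts do not say so:

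- Section 3.8.1 speaks of calculating scores, under a description of how the instrument is scored. The five domain percentages are needed to obtain the total, so the sentence can be read as scoring instructions.
- Section 3.11 speaks of comparing changes between groups. It does not list the scores to be compared.
- Question 2 asks about gross motor function as a whole, and the total is the only one of the six scores that covers all five domains.
- The other fields on the form do not compete seriously. Sections 3.6.1, 3.8.1 and 3.10.1 all name the GMFM-88. The GMFM-66 field needs separate software that the methods do not mention, and the goal total needs goal areas that the methods do not set.

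**Cost of treating all six as formal claims.** Bonferroni gives 0.05/6 = 0.0083. With 20 per arm and an assumed 80% power, the detectable standardised difference is (1.96 + 0.84) × √(2/20) ≈ 0.89 at 0.05, and (2.64 + 0.84) × √(2/20) ≈ 1.10 at 0.0083. Keeping 0.89 would need 2 × (3.48/0.886)² ≈ 31 per arm instead of 20. That is a real loss, to guard against six tests the plan has not said it will run.

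**The case for a change.** The strongest reply is that prespecification exists to remove this kind of freedom. The outcome is called primary, naming the score would take a sentence, and even at correlation 0.9 the chance of some significant score is about twice 5%. At correlation 0.5, about 14% of null trials would show a null total beside a significant domain, which is the pattern the plan does not rule on.

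Part of this stands. No section names the score, and the arithmetic is sound under its condition. The form and the abbreviation list also mention GMFM-66, so six is a minimum count of available scores.

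The condition is where it fails. The figures describe what the wording allows, not what is planned. Section 3.11 fixes a level for each analysis and promises no error rate for question 2 as a family, so no stated guarantee is broken. Question 2 is also directional, which makes 9% against 2.5% the relevant comparison, not 19% against 5%. The model is rough too: domain percentages are bounded, items are ordinal, and GMFCS levels I to IV are enrolled, so floor and ceiling effects are likely and were not examined.

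On aids and orthoses, section 3.6.3 has trained, calibrated assessors who are not involved in the intervention sessions. Nothing in the documents suggests the scoring condition would differ by arm.

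**Conclusion.** No change follows. The plan omits a detail that an analyst would fill sensibly: the GMFM-88 total is the natural score for a question about overall gross motor function, and the domains describe where a change occurred. On that reading question 2 has one between-group test at 0.05, and naming the score would only record what would be done anyway.

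The inflation of about 19% (22% to 10%), or about 9% (11% to 5%) in favour of MFR, is a conditional illustration. It requires all six scores to be tested between arms and any one to count as a yes, and it rests on assumed normal, equally correlated changes. Harm is possible but not shown. A report that claimed success on a single domain beside a null total would be open to challenge, and a reader could see this because the total is among the scores to be calculated.

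This conclusion covers the scores within the GMFM-88 only. It does not address testing GMFM-88, PBS and ROM together as primary outcome measures.
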